#### **Additional sensitivity / supplementary analyses due to COVID-19 for the two co-primary endpoints**

Considerations made by the European Medicines Agency (EMA) and the Food and Drug Administration (FDA) (see Appendix, 8.1) guide possible changes to the statistical analysis due to COVID-19.

The following sensitivity and supplementary analysis will be performed for the two co-primary endpoints and based on the E-MITTv5 population (see Section 3.1.1) to investigate the impact of COVID-19:

- Subgroup analysis by the way of endpoint ascertainment (in-clinic, remote). A subject is assigned to the subgroup with the most visits done with respect to in-clinic or by remote (excluding Baseline and Week 52, which must be performed in-clinic). If a visit was done in-clinic or by remote is documented in the eCRF *Covid-19 Impact Assessment*.
- ADAS-Cog11: Include only the subset of items (for all visits), which can be administered by remote by telephone or video call (see Section 4.5.1).
- ADCS-ADL23: Exclude items which are affected by COVID-19 restrictions (see Section 4.5.1).
- A composite scale designed as a COVID-19 impact free joint score ("COVID-19 Composite Scale") will be analyzed. The included items, selected from ADAS-Cog11 and ADCS-ADL23, are indicated in section 12.2 and result in a score ranging from 0 to 113. Since a higher score for ADAS-cog13 indicates more impairment (less impairment for ADCS-ADL23), the values of ADAS-cog13 will be transformed (maximal score minus actual score) before summarizing over both assessments.
- Subgroup of subjects with / without COVID-19 infection.
- Subgroup of subjects with / without COVID-19 vaccination.

If a subgroup consists of less than 10% of the randomized subjects, only summary statistics will be presented.

Sponsor:	TauRx Therapeutics Ltd.		
Protocol:	TRx-237-039		
Document Version No.:	3.0	Document Date:	07-JUN-2023

### 5.9.2.2. Estimand Analysis

The primary and secondary estimands (see Section 5.9.1.1, and 5.9.1.3) will be analyzed with the ITTv5 population (see Section 3.1.1) using the MMRM as described in the previous section for the MITT population.

With the estimand described in Section 5.9.1.2 the analysis of the primary estimand will be repeated for the ITT population, but without its sensitivity analyses.

Sample SAS code (will be fully validated at the analysis stage):

```

PROC MIXED DATA=dataset METHOD=REML COVTEST;
  CLASS subject treatment(REF='Control') visit severity(REF='moderate') region(REF='Europe')
  prioruse(REF='None');
  MODEL scorediff = treatment/visit severity region prioruse scorebl / SOLUTION CL DDFM=
  KENWARDROGER;
  REPEATED visit / SUB=subject TYPE=UN;
  LSMEANS treatment*visit visit / CL;
  *BY_IMPUTATION_;
  LSMESTIMATE treatment*visit "intervention effect" nw13 nw26 nw39 nw52 -nw13 -nw26 -
  nw39 -nw52 / DIVISOR=Nhmtm CL;
  LSMESTIMATE treatment*visit "intervention effect (sensitivity)" 0 0 0 nw52 0 0 0 -nw52 /
  DIVISOR=Nhmtm CL;
  RUN;

```

*nw0, nw13, nw26, and nw39* are the number of subjects within the respective HMTM treatment group who withdrew for potentially treatment-related reasons (ICE #2 in Section 5.9.1.1), have a non-missing efficacy parameter at Baseline, Week 13 (26, 39), and do not have any on-treatment assessments at any scheduled visit subsequent to Baseline, Week 13 (26, 39). With *Nhmtm* the sample size in the HMTM treatment group, *nw52* is calculated as  $nw52 = Nhmtm - nw0 - nw13 - nw26 - nw39$ . The numbers will need to be calculated before applying the analyses model (for example saved in macro variables). With respect to sensitivity analyses, *nwx* and *nw* will need to be re-calculated, when handling further ICEs as ICE #2.

The secondary estimand is analyzed using an ANCOVA, including the randomization stratification variables (see Section 2.6) as fixed factors, the respective efficacy Baseline value and the total duration of exposure (see Section 5.12.1) as covariates, and the treatment indicator; with the Kenward and Roger method used for calculating the denominator degrees of freedom for the tests of fixed effects.

Sponsor:	TauRx Therapeutics Ltd.		
Protocol:	TRx-237-039		
Document Version No.:	3.0	Document Date:	07-JUN-2023

Sample SAS code (will be fully validated at the analysis stage):

```

PROC MIXED DATA=dataset METHOD=REML COVTEST;
  CLASS subject treatment(REF='Control') severity(REF='moderate') region(REF='Europe')
  prioruse(REF='None');
  MODEL scorediff = treatment severity region prioruse scorebl (duration) / SOLUTION CL DDFM=
  KENWARDROGER;
  LSMEANS treatment / CL;
  LSMESTIMATE treatment "intervention effect at the end of treatment" 1 -1 / CL;
  RUN;

```

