#### 4.5.2. Multiple Imputation

Upscaling will be performed prior to the use of multiple imputation.

Sponsor:	TauRx Therapeutics Ltd.		
Protocol:	TRx-237-039		
Document Version No.:	3.0	Document Date:	07-JUN-2023

Multiple imputation will be performed only for the double-blind treatment phase data of the two co-primary endpoints and the secondary endpoint MRI whole brain volume.

Missing values will be imputed multiple times to account for the uncertainty about the true values to impute. A multivariate imputation by fully conditional specification (FCS) methods will be used, which handles arbitrary missing patterns. This will be applied using the FCS statement in the MI procedure in SAS®.

The imputation model uses the same fixed factors and covariates as in the respective analysis models, unless specified otherwise.

The seed of **237039** was pre-specified in the study protocol and must be used in the final run. A total of 50 imputed datasets will be generated.

For the MITT populations data after multiple imputation are analyzed in a sensitivity analysis. The imputation model will not include the treatment indicator.

Sample SAS code (will be fully validated at the analysis stage):

```
PROC MI DATA=dataset SEED=237039 NIMPUTE=50 OUT=datami;  
  CLASS visit severity region prioruse;  
  FCS REG(adascog11 = visit severity region prioruse adascog11bl);  
  FCS REG(adcsadl23 = visit severity region prioruse adcsadl23bl);  
  FCS REG(mriwbv = visit severity region prioruse mriwbvbl);  
  VAR visit severity region prioruse adascog11bl adcsadl23bl mriwbvbl adascog11 adcsadl23  
       mriwbv;  
  RUN;
```

Imputed values will not be edited to fit their respective definition area, since they are not equivalent to observed data and serve only to help estimating covariances between variables.

In sensitivity analyses of the primary estimand (see Section 5.9.1.1) the following two strategies will be followed, as summarized in Section 4.5.2.1 and 4.5.2.2:

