In another sensitivity analysis the alternative assumption will be investigated, that the subjects withdrawing from treatment for treatment-related reasons do not retain any treatment effect after Baseline; the intervention effect  $I$  in this case is  $I=E*(1-w)$ , where  $E$  is the treatment effect at Week 52 and  $w$  is the fraction of

Sponsor:	TauRx Therapeutics Ltd.		
Protocol:	TRx-237-039		
Document Version No.:	3.0	Document Date:	07-JUN-2023

subjects within the HMTM treatment group who withdraw for a potential treatment-related reason up to Week 52.

**Events 3** will be handled according to the original randomized treatment group assuming they did not start AChEI and/or memantine and will be analyzed the same as ICE #2.

**Events 4** will be handled according to a treatment policy strategy, using data after occurrence of the ICE. A sensitivity analysis will be carried out using the strategy as described for the ICE #2.

**Events 5, 6, and 7** will be handled according to a treatment policy approach, using all data (also after occurrence of respective ICE).

**Events 8** will be handled as treatment failure. If the patient dies prior to Week 52, the missing assessments will be imputed by the population average in decline, calculated by visit, within the control arm.

**Events 9, and 10** will be handled with a hypothetical strategy assuming COVID-19 disease would not have happen, not using data after occurrence of the ICE.

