#### 5.9.1.5. PET Estimand (ITTv5)

The PET Estimand is designed to answer the question on the treatment effect of HMTM dose of 16 mg/day as monotherapy versus control (containing a small amount of MTC) in the targeted population of subjects with *very mild* AD (CDR of 0.5) at Week 52, regardless of trial product discontinuation, based

Sponsor:	TauRx Therapeutics Ltd.		
Protocol:	TRx-237-039		
Document Version No.:	3.0	Document Date:	07-JUN-2023

on the  $^{18}\text{F}$ -FDG-PET temporal lobe in SUVR. If data is available from subjects with other than a CDR of 0.5, these will not be included in the analysis.

This estimand is constructed in line with ICH E9 (R1) addendum. The five components defining the estimand of interest are:

- A. Treatment:** 52 weeks HMTM dose of 16 mg/day or matching control (containing a small amount of MTC) as monotherapy, regardless of adherence.
- B. Population:** Subjects with very mild AD (CDR of 0.5) and as further described by the inclusion and exclusion criteria, randomized under protocol version 5.0 or higher.
- C. Patient-level outcome / variable:** Change from Baseline of the  $^{18}\text{F}$ -FDG-PET temporal lobe in SUVR at Week 52.
- D. Population-level summary:** Population weighted least squares means difference.
- E. Intercurrent Events:** Identification of ICE is as described for the primary estimand (see Section 5.9.1.1).  
**Events 1** will be handled according to a hypothetical strategy as if patients have stayed on treatment.  
In a sensitivity analysis all these subject withdrawals are assumed to be potentially treatment-related, which are then handled using the treatment policy approach from ICE #2.  
**Events 2** will be handled using a treatment policy approach assuming that the subjects withdrawing from treatment for treatment-related reasons do not retain any treatment effect after Baseline; the intervention effect / in this case is  $I=E*(1-w)$ , where  $E$  is the treatment effect at Week 52 and  $w$  is the fraction of subjects within the HMTM treatment group who withdraw for potentially treatment-related reasons up to Week 52.  
**Events 3** will be handled according to the original randomized treatment group assuming they did not start AChEI and/or memantine and will be analyzed the same as ICE #2.  

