#### Estimand analysis

The PET estimand (see Section 5.9.1.5) will be estimated using the ANCOVA as described previously for the MITT population.

Sample SAS code (will be fully validated at the analysis stage):

```

PROC MIXED DATA=dataset METHOD=REML COVTEST;
  CLASS subject treatment(REF='Control') severity(REF='moderate') region(REF='Europe')
  prioruse(REF='None');
  MODEL scorediff = treatment severity region prioruse scorebl / SOLUTION CL
  DDFM=KENWARDROGER;
  LSMEANS treatment / CL;
  LSMESTIMATE treatment "intervention effect" nw52 -nw52 / DIVISOR=Nhmtm CL;
  RUN;

```

Sponsor:	TauRx Therapeutics Ltd.		
Protocol:	TRx-237-039		
Document Version No.:	3.0	Document Date:	07-JUN-2023

With  $nw$  the total number of subjects who withdrew for potentially treatment-related reasons during the study until Week 52 in the respective HMTM group and  $Nhmtm$  the total sample size in the HMTM group, then  $nw52 = Nhmtm - nw$ . The numbers will need to be calculated before applying the analyses model (for example saved in macro variables).

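### The no-retained-effect contrast has the same p-value whatever the withdrawal fraction, so it cannot serve as a significance check; for FDG-PET the same rescaling is the main PET-estimand test

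*SAP*

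**What the plan says.** **Co-primary endpoints.** In SAP 5.9.1.1, treatment-related withdrawal (intercurrent event 2) is handled in the main analysis by letting withdrawers keep the effect reached at their last on-treatment visit. The contrast in 5.9.2.2 mixes the four visits: "LSMESTIMATE treatment*visit 'intervention effect' nw13 nw26 nw39 nw52 -nw13 -nw26", and so on.

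One sensitivity analysis takes the opposite assumption, that "the subjects withdrawing from treatment for treatment-related reasons do not retain any treatment effect after Baseline". Its effect is I = E*(1-w), with E the Week 52 effect. The code uses only the Week 52 coefficients: "LSMESTIMATE treatment*visit 'intervention effect (sensitivity)' 0 0 0 nw52 0 0 0 -nw52", with the HMTM arm size as divisor. The weight is "nw52 = Nhmtm - nw0 - nw13 - nw26 - nw39". The counts are set in advance: "The numbers will need to be calculated before applying the analyses model (for example saved in macro variables"). Protocol 17.4.11.7 describes the same formula, also as a contrast.

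For the same event, 5.9.1.1 also plans two imputation analyses, one based on control data (4.5.2.1) and one on each arm's own data (4.5.2.2).

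**FDG-PET.** In SAP 5.9.1.5 the zero-retention rule is the main handling of event 2, "assuming that the subjects withdrawing from treatment for treatment-related reasons do not retain any treatment effect after Baseline". The estimand code in 5.9.3.2 is the single Week 52 difference times nw52 over the arm size.

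**Imputation scope.** SAP 4.5.2 says "Multiple imputation will be performed only for the double-blind treatment phase data of the two co-primary endpoints" and MRI whole brain volume.

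**The concern.** An analysis that assumes withdrawers lose all benefit is the harsher alternative to full retention. A reader will look at whether significance survives it, because SAP 4.1 tests the primary and secondary endpoints at two-sided 0.05. If the p-value cannot respond to the amount of withdrawal, that survival says nothing beyond the Week 52 test itself. For FDG-PET the stake is larger, because the rescaled contrast is the main estimand analysis and not one check among several.

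**Working it through.** **1. Algebra.** Let E be the Week 52 difference, S its standard error, and c = nw52/Nhmtm = 1-w, a fixed number.

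- Estimate: c*E. Standard error: c*S.
- t = (c*E)/(c*S) = E/S for every w below 1.
- Kenward-Roger degrees of freedom for a one-row contrast do not change when the row is multiplied by a constant. Rubin's rules do not alter this either: within- and between-imputation variances both scale by c squared.
- The hypothesis c*E = 0 is the hypothesis E = 0.

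**2. A realistic standard error.** SAP 5.3 gives, for ADCS-ADL23, SD 8.5, an effect of 3.4, 200 per arm, 20% to 25% withdrawal and about 93.2% power. With 200 x 0.75 = 150 per arm, the noncentral t power is 0.9323, which reproduces the figure. The ADAS-cog11 figure of 96.7% reproduces the same way (0.9674). So S = 8.5 x sqrt(2/150) = 0.9815.

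**3. The planned contrast at an assumed observed effect of 1.95** (298 degrees of freedom):

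| w | Estimate | SE | 95% CI | t | p |
|---|---|---|---|---|---|
| 0 | 1.95 | 0.981 | 0.018 to 3.882 | 1.987 | 0.048 |
| 0.10 | 1.755 | 0.883 | 0.017 to 3.493 | 1.987 | 0.048 |
| 0.25 | 1.462 | 0.736 | 0.014 to 2.911 | 1.987 | 0.048 |
| 0.40 | 1.170 | 0.589 | 0.011 to 2.329 | 1.987 | 0.048 |
| 0.90 | 0.195 | 0.098 | 0.002 to 0.388 | 1.987 | 0.048 |

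The interval narrows towards zero but never reaches it. Adding binomial variance for w (delta method, N = 200) changes little: p = 0.0481 at w = 0.10 and 0.0486 at w = 0.25.

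**4. Against the retained-effect contrast.** One simulated data set was fitted with an unstructured covariance. Assumptions: 200 per arm; visit effects 0.2, 0.7, 1.4 and 2.4; SDs 4.5, 6, 7.3 and 8.5; correlation 0.65 per visit step; 22.5% dropout; normal reference distribution. Only the weights were then varied, with withdrawals split equally over Baseline and Weeks 13, 26 and 39.

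| w | No retention: estimate (SE) | p | Retention: estimate (SE) | p |
|---|---|---|---|---|
| 0 | 2.385 (0.971) | 0.014 | 2.385 (0.971) | 0.014 |
| 0.10 | 2.146 (0.874) | 0.014 | 2.163 (0.898) | 0.016 |
| 0.225 | 1.848 (0.752) | 0.014 | 1.886 (0.810) | 0.020 |
| 0.40 | 1.431 (0.583) | 0.014 | 1.499 (0.692) | 0.030 |
| 0.60 | 0.954 (0.388) | 0.014 | 1.055 (0.569) | 0.063 |

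The harsher assumption gives the smaller estimate and the smaller p-value. The direction depends on the effect profile; here the effect builds late.

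**5. FDG-PET.** The estimand contrast in 5.9.3.2 is nw52/Nhmtm times a 1, -1 contrast from the same ANCOVA fit, so step 1 applies directly. Treating non-treatment-related withdrawals as treatment-related (the sensitivity in 5.9.1.5) enters the contrast only through a larger w.

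**6. Is PET imputed?** The passages side by side:

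- SAP 4.5.2 confines imputation to the co-primaries and MRI whole brain.
- SAP 5.9.3.2 gives PET the supplementary and sensitivity analyses of 5.9.2.1 apart from the model-based ones involving time, and that list includes multiple imputation.
- SAP 4.5 applies imputation to hypothetical strategies, which the PET estimand uses for some events.
- Protocol 17.4.11.5.1 provides extra variables for imputing endpoints without several planned post-baseline assessments.
- SAP Section 10 records no change.

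Even on the wider reading, the version reached through 5.9.2.1 is the MITT imputation, whose model omits treatment. SAP 5.9.1.5 lists no control-based run for PET.

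**The case against.** The strongest reply is that nothing is miscalculated. With w treated as fixed, (1-w)*E = 0 is the same null as E = 0, so an unchanged p-value is expected. The scaled standard error is also about right for this estimator. With SD 5.9, 200 per arm and 20% missing it is 0.8 x 5.9 x sqrt(2/160) = 0.53. In a re-run of that setting, the actual sampling SD of the control-based imputation estimate was also 0.53, while Rubin's rules gave 0.65. Under no effect, the scaled contrast rejected in 5.2% of runs and Rubin's rules in 1.5%. This stands. A reader might infer that the scaled contrast hides fragility, or that its standard error should be kept at full size. The first inference mistakes Rubin conservatism for fragility, and the second matches no planned estimator.

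Other parts of the reply that stand:

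- The attenuated estimate is visible, and SAP 5.9.1.1 calls it only an alternative assumption. Neither document claims significance under a most conservative case.
- The co-primaries already have control-based imputation for this event, and 5.9.1.4 extends it to MRI whole brain. Their p-values can move there.
- Invariance holds within one fit. The PET estimand data differ from the MITT data (imputed deaths, excluded post-COVID data), so its p-value need not equal that of the MITT ANCOVA. Reclassifying events can also move p if it changes which data enter.
- The wording "the total sample size in the HMTM group" might suggest that the PET weight is taken over the whole arm. SAP 5.9.1.5 and 5.9.3.2 restrict that analysis to CDR 0.5, so the documents do not support that reading.

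The reply does not give the p-value of the rescaled contrast any information about w.

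**Conclusion.** The point holds as an exact result. For a given fit, fixed weights and w below 1, the p-value of I = E*(1-w) does not change with w, and neither does whether its interval excludes zero. Only the estimate and interval width shrink. As a significance check it adds nothing to the Week 52 test, and it can look stronger than the analysis it is meant to stress.

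For the co-primaries and MRI whole brain this is one uninformative check beside informative ones. FDG-PET is the weaker case: w cannot affect the main PET-estimand test, and the documents conflict on whether any imputation stands behind it. A reader might infer that the trial's primary test is affected, or that PET certainly has no imputation. Neither is supported. PET is a secondary endpoint, the SAP's Primary Estimand covers ADAS-cog11 and ADCS-ADL23 with the retained-effect contrast, and the PET imputation text is contradictory rather than absent.

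The documents do not give the fraction of treatment-related withdrawals. The 20% to 25% in SAP 5.3 is for all withdrawals, so the w values, observed effects and visit profile above are assumptions. The invariance does not depend on them.

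**What to change.** 1. In SAP 5.9.1.1 and 5.9.2.2, report I = E*(1-w) as a descriptive, attenuated effect size without a p-value. Name the control-based imputation of 4.5.2.1 as the significance check for treatment-related withdrawal. It is already planned; the SAP notes that its sample code is still to be validated.
2. Reconcile SAP 4.5.2 with SAP 5.9.3.2 and Protocol 17.4.11.5.1, and add a control-based imputation sensitivity analysis for Week 52 FDG-PET.

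The cost is SAP wording and one extra imputation run. Standard errors from Rubin's rules are conservative under control-based imputation, so the PET result may look less favourable. State this beforehand, so that a larger p-value is not read wholly as a loss of effect.

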### **13.1 AChEI and/or Memantine**

Subjects are not to be treated with an AChEI and/or memantine within the 60 days prior to the baseline assessments (inclusive of the baseline F-FDG-PET scan in subjects who have a screening CDR of 0.5). If a subject decides to discontinue AD medication in order to enter

the study, a letter will be sent to his/her primary care physician informing him/her of the subject's decision. The withdrawal / discontinuation of AD medication for study inclusion should not occur until the subject has been confirmed eligible for the study.

If a subject begins an AChEI and/or memantine during the study, LMTM will be discontinued and LMTM will not be made available *via* the EAP. Subjects will be encouraged to continue with scheduled assessments if willing to do so without LMTM. Handling of data for such subjects is described in Section 17.4.11.3.

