## 5. STATISTICAL ANALYSIS OF DOUBLE-BLIND TREATMENT PHASE

In the following, *decline* is defined as a change into the direction of greater impairment. An *on-treatment visit*, and their corresponding assessments, is defined as a visit where a subject was on investigational product (within the last 14 days) and not on any AchEI and/or memantine (except short-term use). This means, in case of a longer dose interruption a visit can be off-treatment if the subject was not on-treatment within the last 14 days of the visit.

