#### 5.9.1.1. Primary Estimand (ITTv5)

The Primary Estimand is designed to answer the question on the treatment effect of HMTM dose of 16 mg/day as monotherapy versus control (containing a small amount of MTC, spiked) in the targeted

---

Sponsor:	TauRx Therapeutics Ltd.		
Protocol:	TRx-237-039		
Document Version No.:	3.0	Document Date:	07-JUN-2023

population of subjects with probable AD and MCI-AD at Week 52, regardless of trial product discontinuation, based on the two co-primary endpoints.

This estimand is constructed in line with ICH E9 (R1) addendum. The five components defining the estimand of interest are:

**A. Treatment:** 52 weeks HMTM dose of 16 mg/day or matching control (containing a small amount of MTC) as monotherapy, regardless of adherence.

**B. Population:** Subjects with probable AD and MCI-AD as described by the inclusion and exclusion criteria, randomized under protocol version 5.0 or higher.

**C. Patient-level outcomes / variables:** The co-primary outcomes are the change from Baseline of the ADAS-cog11 and ADCS-ADL23 at Week 52.

**D. Population-level summary:** Population weighted least squares means difference.

**E. Intercurrent Events:** The following ICE have been identified which could prevent measurement of the primary outcome or change the interpretation of the measured primary outcome:

1. Subjects withdraw from study before the completion of 52 weeks treatment phase for non-treatment related reason
2. Subjects withdraw from study before the completion of 52 weeks treatment phase for treatment related reason
3. Initiation of AChEI and/or memantine
4. Study treatment discontinuation for any reason other than initiation of AChEI and/or memantine (including discontinuation by the Investigator if he/she judges that treatment is no longer appropriate, if the subject's clinical condition is worsening, or for AE, or due to study drug dose interruption longer / more frequent than specified in ICE #5 below) (TOTOs, see Section 4.4)
5. A dose interruption for more than 14 consecutive days or more than two occasions of dose interruptions up to a maximum of 14 consecutive days due to safety concerns and initiated by the PI (see Section 4.4)
6. Intercurrent illnesses, or initiation of medical food or medications not allowed by protocol (which will be identified during the BDRM)

Sponsor:	TauRx Therapeutics Ltd.		
Protocol:	TRx-237-039		

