Document Version No.:	3.0	Document Date:	07-JUN-2023

- 7. Study treatment non-compliance, defined as <80% or >120% taking into consideration any dose interruptions (if this cannot be estimated, it does not result automatically in a non-compliance)
- 8. Deaths before the completion of 52 weeks treatment phase
- 9. COVID-19 infection
- 10. Death due to COVID-19

**Events 1** will be handled according to a hypothetical strategy as if patients have stayed on treatment.

In a sensitivity analysis all these subject withdrawals are assumed to be potentially treatment-related, which are then handled using the treatment policy approach from ICE #2.

**Events 2** will be handled using treatment policy approach reflecting Copy Incremental from Reference strategy (using data after occurrence of the ICE for the estimation, if available). Subjects who withdraw for treatment-related reasons are assumed to retain 100% of the treatment effect they had attained up to the point of withdrawal but do not continue to benefit from treatment afterwards, in other words, assuming that the clinical course post ICE for either treatment group follows control treatment group. This corresponds to the estimate  $I = (E0*w0 + E13*w13 + E26*w26 + E39*w39) + E52*(1-w0-w13-w26-w39)$ , where for instance  $E13$  is the treatment effect at Week 13 and  $W13$  is defined as the fraction of subjects who withdrew for a potential treatment-related reason, have a non-missing efficacy parameter at Week 13, and do not have any on-treatment assessments at any scheduled visit subsequent to Week 13. The fractions are calculated within the HMTM treatment group.  $W0$  refers to subjects who had no measurement taken after the baseline measurement and thus  $E0$  is zero. The estimate  $I$  will be reported as the intervention effect and will be calculated using a contrast on the LSM (see Section 5.9.2.1).

Two sensitivity analyses will be run using hypothetical strategies (not using data after occurrence of the ICE), one by imputing missing data for both treatment groups based on data seen in control group, and one by imputing missing data for each treatment group based on data seen in their own group (see Section 4.5.2).

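### As written, the withdrawal counts behind the EMA intervention effect are not mutually exclusive, so some subjects can be subtracted from the Week 52 weight more than once

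*SAP*

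**What the plan says.** SAP 5.9.1.1 defines the intervention effect as I = E0·w0 + E13·w13 + E26·w26 + E39·w39 + E52·(1 - w0 - w13 - w26 - w39), with the fractions taken within the HMTM arm. The Week 13 fraction covers treatment-related withdrawers who "have a non-missing efficacy parameter at Week 13, and do not have any on-treatment assessments at any scheduled visit subsequent to Week 13".

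SAP 5.9.2.2 turns the fractions into counts. A subject is counted at a visit if any score is available there, with no mention of treatment status at that visit. The other condition is that they "do not have any on-treatment assessments at any scheduled visit subsequent to Baseline, Week 13 (26, 39"). The section then sets "nw52 = Nhmtm - nw0 - nw13 - nw26 - nw39". A second contrast in the same code uses nw52 alone. It implements the sensitivity analysis that 5.9.1.1 defines as E*(1-w).

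The opening of SAP Section 5 defines an on-treatment visit as "a visit where a subject was on investigational product (within the last 14 days) and not on any AchEI and/or memantine".

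The handling rules in SAP 5.9.1.1 determine who is counted:
- **ICE #2** is "Subjects withdraw from study before the completion of 52 weeks treatment phase for treatment related reason". Data after the event are used where available.
- **ICE #3**, starting an AChEI or memantine, "will be analyzed the same as ICE #2".
- **ICE #4**, stopping drug for another reason, is handled by treatment policy. It is handled as ICE #2 only in a sensitivity analysis.

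On attendance after starting an AChEI or memantine, Protocol 13.1 says: "Subjects will be encouraged to continue with scheduled assessments if willing to do so without LMTM".

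Protocol 17.4.3 limits the EMA model to scheduled on-treatment visits. Protocol 17.4.4 excludes data after the event for ICE #3 and for the EMA handling of ICE #4, although it uses them for ICE #2. SAP 5.9.1.1 repeats neither the restriction nor these exclusions.

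**The concern.** Subtracting four counts from the arm size gives a head count only if no subject is in two of them. The rule does not ensure this. It asks for any score at the index visit, on or off drug, and for no on-treatment assessment afterwards. Once a counted subject has gone off treatment, every later visit up to Week 39 at which they are scored meets the same two conditions. Each extra count takes one unit of weight from E52 and gives it to an earlier visit, or to Week 0 where the effect is zero.

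This contrast is the EMA primary estimate for both co-primary endpoints. It is reused for the MRI estimands and for the 8 mg/day comparison. The PET estimand is not affected, because SAP 5.9.3.2 subtracts a single total of withdrawers.

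**Working it through.** **Inputs from the documents.** About 200 subjects per arm and an ADAS-cog11 effect of 2.6 units (SAP 5.3). The plan prints no weights to reproduce. The section supplying these inputs does reproduce: 150 per arm (200 less 25%), noncentral t, two-sided 0.05, gives 93.2% power for ADCS-ADL23 and 96.7% for ADAS-cog11, as stated.

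**Assumptions not in the documents.** The effect grows linearly, so E13, E26 and E39 are 0.65, 1.30 and 1.95. Last on-treatment visits are spread evenly over Baseline and Weeks 13, 26 and 39. The number affected and their off-treatment attendance are varied.

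**Step 1: times one subject is counted under 5.9.2.2, if scored off drug at every later visit.** The contribution is the sum of the effects at the counted visits, plus (1 - number of counts) × E52.

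| Last on-treatment visit | Counted in | Times | Contribution, literal | Contribution, counted once |
|---|---|---|---|---|
| Baseline | nw0, nw13, nw26, nw39 | 4 | -1.50 × E52 | 0 |
| Week 13 | nw13, nw26, nw39 | 3 | -0.50 × E52 | 0.25 × E52 |
| Week 26 | nw26, nw39 | 2 | 0.25 × E52 | 0.50 × E52 |
| Week 39 | nw39 | 1 | 0.75 × E52 | 0.75 × E52 |

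A subject with no off-treatment score is always counted once.

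**Step 2: 20 affected subjects, full off-treatment attendance.**
- Counted once: 5 at each of the four visits, nw52 = 180. I = [5 × (0.65 + 1.30 + 1.95) + 180 × 2.6] / 200 = 487.5 / 200 = 2.4375.
- Literal: nw0 = 5, nw13 = 10, nw26 = 15, nw39 = 20, so nw52 = 200 - 50 = 150. I = [10 × 0.65 + 15 × 1.30 + 20 × 1.95 + 150 × 2.6] / 200 = 455 / 200 = 2.275.
- Difference: -0.1625, or 6.7% of 2.4375.

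**Step 3: other counts.** With 10 affected subjects, 2.4375 against 2.51875, a shift of -0.08. With 20 of whom half attend off drug, 0.90625 × 2.6 = 2.356 against 2.4375, again -0.08. With no off-treatment attendance the two counts agree.

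**Step 4: the second contrast.** In the Step 2 scenario w = 20/200 = 0.10, so E*(1-w) = 0.90 × 2.6 = 2.34. The code gives 150/200 × 2.6 = 1.95, which is 16.7% too small.

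**Step 5: W0.** SAP 5.9.1.1 reserves W0 for subjects with no measurement after Baseline; 5.9.2.2 requires only no later on-treatment assessment. On the first reading, Step 2 has nw0 = 0 and nw52 = 155, so I = (65 + 403) / 200 = 2.34, against 2.275 on the second.

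**Step 6: how a study withdrawer can be counted twice.** SAP 5.5 reassigns scores by study day. Suppose a Week 13 visit on day 92, last dose on day 120 and an early-termination assessment on day 140. That assessment is 20 days after the last dose, hence off-treatment, and falls in the Week 26 window (days 138 to 228). The subject is in both nw13 and nw26.

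**The case against.** The best case for the plan is that a head count was plainly intended and that few subjects could be miscounted.

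- **Intent.** SAP 4.4 speaks of the fraction who withdrew at a given time, and a person withdraws once. E*(1-w) matches the code only if the four counts add up to people. The code is labelled a sample to be validated. This shows what was meant, but it does not change the stated rule, and validating code against that rule would not correct it.
- **Protocol 17.4.3.** With only on-treatment visits in the data, the counts are disjoint. That is correct, but the SAP does not carry the restriction over, and both documents use data after the event for ICE #2. SAP Section 10 lists no departure from the protocol on this point, so the texts are unreconciled.
- **ICE #3.** Protocol 17.4.4 discards scores after the start of an AChEI or memantine, and the SAP's assumption that the drug was not started fits poorly with keeping them. If they are discarded, the subject is counted once. The SAP's actual instruction, however, is to treat these subjects as ICE #2, where later data are kept.
- **ICE #2.** Protocol 11.4.2 asks for a visit as soon as possible after the last dose, so most withdrawers will have no off-treatment score. This stands. Five subjects last on drug at Week 13 with one extra score at Week 26 would move the estimate by 5 × (1.3 - 2.6) / 200 = -0.03.
- **Direction.** If the effect grows over time, the shift is toward zero and does not create a false positive. That is conditional on the shape of the effect, and the result would still not estimate the strategy described.

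A reader might infer that anyone who stops drug and keeps attending distorts the primary estimate. The documents do not support that. Such a subject is ICE #4, handled by treatment policy in the SAP's primary estimand. They are in none of the four withdrawal counts, remain in nw52, and are miscounted only in the ICE #4 sensitivity analysis.

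**Conclusion.** The definition is wrong as written. In the primary contrast it reaches AChEI/memantine starters who keep attending, if their later scores are retained, and treatment-related study withdrawers with an off-treatment assessment before leaving. The second contrast inherits the error through nw52.

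The size cannot be fixed from the documents. Under the stated assumptions the shift is about -0.08 units for 10 affected subjects and -0.16 for 20, and zero if nobody is scored off drug. For scale only, 10 and 20 are 5% and 10% of an arm of 200. These are the shares of AChEI/memantine starters that trigger extra analyses in SAP 5.9.2.1 and Protocol 17.4.11.3; they are not forecasts.

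It would be tempting to read 2.275 against 2.4375 as a demonstrated error in the primary result. It is a scenario: the number affected, their timing, full attendance and linear growth are all assumed, and the documents do not show how the counts were programmed.

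**What to change.** In SAP 5.9.1.1 and 5.9.2.2, state that each HMTM subject handled as ICE #2 is assigned exactly once, to the last scheduled visit with a non-missing on-treatment value, or to Week 0 if there is none. Use that definition for W0 and nw0 in both sections. Add a check that nw0 + nw13 + nw26 + nw39 equals the number of distinct subjects counted.

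Reconcile the SAP's use of data after the event for ICE #2 and ICE #3 with Protocol 17.4.3 and 17.4.4. In the same pass, settle ICE #4, since Protocol 17.4.11.4 treats all off-treatment subjects as terminated for the EMA analysis and the SAP does so only as a sensitivity.

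SAP version 3.0 postdates the partial unblinding for the double-blind analysis (SAP Section 10). The sponsor should therefore document how the counts were actually programmed and, if the literal rule was used, report both results.

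The cost is one sentence in each of two sections, a line of programming and a short note for the study report. No new data are needed.
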